Evaluation methods & sample size	
1) Health facility surveillance. Our malaria surveillance programme supports training in data management and high-quality laboratory testing (microscopy or rapid diagnostic tests) on all patients with suspected malaria. Using this surveillance system, we have developed a method to estimate the incidence of malaria in target areas around the MRCs, providing a direct measure of the burden of malaria. For all patients presenting to the MRCs, information on the location of their residence will be collected. Estimates of malaria incidence will be calculated by dividing the number of laboratory-confirmed malaria cases diagnosed at each MRC (among patients residing in the target area per unit time) by the total population of the MRC target area. To evaluate the impact of the intervention, we will estimate malaria incidence at the MRCs for the 24 months after LLIN distribution.
 
2) Enumeration and census surveys. To estimate the population of the MRC target areas, and to generate a sampling frame for the first community survey (to be carried out 12 months after LLIN distribution), we will enumerate and map all households within each MRC target area. To derive a more accurate estimate of the population of the MRC target areas, we will conduct a census survey of the MRC target areas, concurrently with the first cross-sectional survey.
 
3) Cross-sectional community surveys. Shortly after LLIN distribution (in selected clusters) and at 12 and 24 months following LLIN distribution, randomly selected households will be surveyed from each of the 64 clusters. The survey will include a household questionnaire and clinical & laboratory evaluation of children aged 2-10 years. We will survey 50 households in each cluster (n=3,200), aiming to recruit all eligible children in each household (approximately 5,760) per survey. In 32 clusters (one per district), we will enroll residents of all ages from participating households into the clinical survey, to estimate the impact of COVID-19 on malaria during the 12-month survey.
 
4) Entomology surveys. Funding permitting, mosquitoes from 10 randomly selected households in all 64 clusters will be collected using prokopack aspirators to estimate malaria vector density, and to collect samples for monitoring of insecticide resistance. Collections will be carried out alongside the cross-sectional surveys.
 
5) Economic evaluation. Cost-effectiveness will be assessed at the end of the study by collecting cost data for materials and labour and using effectiveness data to estimate the number of malaria cases averted. Incremental cost-effectiveness ratios (USD per disability-adjusted life year averted and per malaria case averted) will be the primary outcomes.
 
6) LLIN survivorship and durability. At 12 and 24 months after distribution of nets, we will quantify net survivorship in the cross-sectional surveys and (if funding is available) will withdraw (and replace) a subset of LLINs to assess durability using standard WHO methodology.

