Primary outcome	The primary outcome will be malaria incidence within the total population of the MRC target areas.
Secondary outcomes	
1) Community surveys: In all clusters, prevalence of parasitaemia (in children aged 2-10 years) and prevalence of anaemia (haemoglobin < 11 g/dL in children 2-4 years). In selected clusters (n=32), during the 12-month survey, prevalence of parasitaemia (all ages & stratified by age), and prevalence of antibody responses, suggesting prior exposure to SARS-CoV-2 antigens (COVID-19)
 
2) Entomology surveys: Malaria vector density (if funding is available)
 
3) Economic evaluation: Incremental cost-effectiveness ratios (USD per disability-adjusted life year averted and per malaria case averted)
 
4) LLIN survivorship and durability: Survivorship: prevalence of nets present, and in use; Durability: proportionate hole index (subject to available funding)

Study personnel and institutions

Investigators

[name], MD, PhD, DTM&H

Role in project: Principal investigator

Professor of Malaria & Global Health, London School of Hygiene & Tropical Medicine, UK

Infectious Diseases Research Collaboration, Kampala, Uganda

Email: [contact]

[name], MBChB, MPH, PhD

Role in project: Co-PI, Uganda site investigator

Professor, Department of Medicine, Makerere University, Kampala, Uganda

Executive Director, Infectious Diseases Research Collaboration, Kampala, Uganda

Email: [contact]

[name], MD, PhD

Role in project: Co-investigator

Professor, Department of Medicine, University of California, San Francisco, USA

Infectious Diseases Research Collaboration, Kampala, Uganda

Email: [contact]

[name], MBChB, MSc, PhD

Role in the project: Co-investigator

Lecturer, Department of Medicine, Makerere University, Kampala, Uganda

Epidemiologist, Infectious Diseases Research Collaboration, Kampala, Uganda

Email: [contact]

[name], MBChB, MSc

Role in the project: Co-investigator

National Malaria Control Division, Uganda Ministry of Health, Kampala, Uganda

Infectious Diseases Research Collaboration, Kampala, Uganda

Email: [contact]

[name], MA, MSc, PhD, FRES

Role in project: Co-investigator

Professor of Evolutionary Genetics, Liverpool School of Tropical Medicine, UK

Email: [contact]

[name], MD, MA

Role on project: Co-investigator

Associate Professor, Department of Medicine, University of California, San Francisco, USA

Email: [contact]

[name], MD

Role on project: Co-investigator

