5.2 Household registration and LLIN distribution

A key aspect of the distribution will be to ensure that the community members receive the correct number of LLINs. The LLINs will be stored centrally at the National Medical Stores warehouses in Entebbe, and then transferred from the central location to sub-county stores, and then onward to the household. A 'door to door' model of LLIN delivery will be applied with registration and LLIN distribution carried out concurrently. The processes will be handled by a multidisciplinary team, comprised of 5 individuals including: village health team member (VHT)/data clerk, security personnel, Local Council 1 (LC1), and two LLIN carriers. On average, there will be two teams per village for rural settings and four teams per village for urban settings, including towns and municipalities.

The Electronic Data Management Information System (EDMIS) will be used for data management including the following: (1) collection of household-level registration data; (2) establishment of household LLIN need; (3) allocation of number of LLINs for each household; and (4) assignment of household Chalk ID. The VHTs/data clerk will interview the head of household if available, or another adult resident, using the EDMIS electronic system. Information collected will include: (1) name of the household head; (2) National ID number of the head of household; (3) number of residents; (4) number of children under 5 years of age; (5) number of pregnant women; (6) sleeping places available; and (7) the telephone number for the household (if available). The EDMIS electronic system will then generate the Chalk ID and allocate LLINs automatically for each household based on the registration data. The assigned Chalk ID will be written on the household and the allocated LLINs issued to the head of household, or another adult resident,

immediately. The household LLIN distribution will be based on household population with one LLIN distributed for every two people living in the household. The recipient of the LLINs will acknowledge receipt using an appropriate method.

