9.1 Overview

Funding permitting, a sub-set of LLINs distributed during the 2020-2021 universal LLIN campaign will be withdrawn (and replaced) from households enrolled into the 12- and 24-month cross-sectional community surveys to assess net durability. During each community survey, 248 households (4 per cluster, 124 per study arm), will be randomly selected from the 64 clusters to participate in the net durability study and will have one net withdrawn for durability assessment. A sample of 124 nets (one per household) of two different types, PPF LLINs (Royal Guard) and PBO LLINs (PermaNet 3.0) will be collected, packaged, labelled and stored. Each net collected will be replaced by a new net of the same type set aside by the NMCP/Ministry of Health.

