9.2 Net integrity

Net integrity will be assessed using standard WHO guidelines [56]. The nets will be assessed by counting the number of holes (including tears in the netting and spilt seams) by their location on the net and their size.

Holes will be classified into the following categories:

- Smaller than a thumb (0.5-2cm)
- Larger than a thumb, but smaller than a fist (2-10cm)
- Larger than a fist, but smaller than a head (10-25cm)
- Larger than a head (>25cm)

Holes less than 0.5cm will be ignored. Evidence of repairs to the net fabric and the type of repair will be noted and recorded. Net use, care and repair will be emphasised as part of this process. Novel net durability assessment procedures are being developed by a number of transnational research groups and may be incorporated into the LLIN integrity assessments. The new assessments will not affect net replacement, measurement, or storage protocols.

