13.1 Outcome measures

The primary outcome of the study will be malaria incidence (defined as the number of cases of laboratory-confirmed malaria diagnosed at the MRC among patients residing in the target area, per unit time over the 24-month follow-up period, divided by the total population of the target area) in patients of all ages.

Secondary outcomes will include:

- 1 Cross-sectional surveys: Prevalence of parasitaemia (in children aged 2-10 years; in selected clusters, in individuals of all ages), prevalence of anaemia (haemoglobin < 11 g/dL in children 2-4 years), LLIN ownership (the proportion of households that owned at least one LLIN), adequate LLIN coverage (the proportion of households that owned at least one LLIN for every two occupants), LLIN access (the proportion of residents who could sleep under a LLIN if each LLIN in the household were used by up to two residents) and LLIN use (the proportion of household residents who slept under an LLIN the previous night); in selected clusters, seroprevalence of COVID-19
- 2 Entomology surveys (funding permitting): Vector density, and insecticide resistance marker frequency variation
- 3 LLIN integrity and chemical analysis of LLINs (funding permitting): LLIN integrity: number and estimated area of holes in the net fabric; Chemical analysis of LLINs: total concentration of insecticide and or synergist remaining on each net to be measured
- 4 Economic evaluation: Incremental cost-effectiveness ratios (USD per disability-adjusted life year averted and per malaria case averted)

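### Net integrity is compared between arms only among campaign nets that can still be withdrawn, and no planned analysis joins it to net loss

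*Protocol*

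**What the plan says.** Protocol 9.1 states that, funding permitting, a subset of campaign nets "will be withdrawn (and replaced) from households enrolled into the 12- and 24-month cross-sectional community surveys to assess net durability". The sample per survey is "248 households (4 per cluster, 124 per study arm), will be randomly selected from the 64 clusters", and each selected household "will have one net withdrawn for durability assessment". Under 9.2, "The nets will be assessed by counting the number of holes (including tears in the netting and spilt seams"), by size and position on the net.

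Section 13.1 lists the outcome as "LLIN integrity: number and estimated area of holes in the net fabric". Section 13.5 compares integrity between arms by regression with generalized estimating equations and reports a density or rate ratio.

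Net loss appears elsewhere. The synopsis says "we will quantify net survivorship in the cross-sectional surveys" and lists two outcomes side by side: "Survivorship: prevalence of nets present, and in use; Durability: proportionate hole index (subject to available funding"). Secondary objective 3 also names attrition. However, survivorship is not among the outcomes in 13.1 and has no stated model in 13.5. The SAP carries neither survivorship nor integrity; its net outcomes (2.2.2 and 8.2) are ownership, coverage, access and use.

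Neither document says how a selected household with no campaign net left is handled.

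**The concern.** Whether a net is still available is determined after randomisation, and damage is one plausible reason for its absence. If households throw away badly torn nets, the nets left for assessment are the better ones, and the degree of selection may differ between net types. The arm that discards more of its torn nets then looks better on hole number and area.

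The protocol gives grounds for expecting loss to be substantial. Section 1.3 reports household ownership of at least one LLIN falling from 94% to 65% over three years, and section 1.9 cites a durability study in which survivorship of a PPF net and its comparator was poor at 36 months. Neither says how much of the loss was due to damage.

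At stake is the durability comparison in objective 3. There is also a smaller, optional consequence: section 10.1 allows additional economic analyses with a shorter net lifespan based on durability data.

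**Working it through.** **The plan's own figure.** The only number given for this component is the sample. Four nets per cluster in 64 clusters is 4 × 64 = 256, or 4 × 32 = 128 per arm, against the stated 248 and 124. The stated figures fit 62 clusters (4 × 62 = 248; 4 × 31 = 124). This should be corrected, but it is a separate inconsistency. No power, effect size or attrition rate is given for integrity, so there is nothing further to reproduce.

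**Illustration on hole area.** All inputs are assumptions; the documents give none of them.
- Hole area per net is lognormal with log-SD s = 1.5 and median m = 150 cm² in arm X and 225 cm² in arm Y.
- The serviceable limit is L = 600 cm².
- A fraction d of nets beyond the limit is discarded, and no other nets are lost.
- The planned ratio is taken as a ratio of mean hole areas, Y/X.

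Formulas:
- Mean over all nets: M = m·exp(s²/2), giving 462.0 and 693.0 cm². True ratio 1.50.
- Serviceable share of all nets: F = Φ(ln(L/m)/s), giving 82.2% and 74.3%.
- Part of M from nets within the limit: A = M·Φ((ln(L/m) − s²)/s), giving 130.5 and 137.7. The rest, B = M − A, is 331.6 and 555.3.
- Mean among available nets: [A + (1−d)B] / [F + (1−d)(1−F)].
- Share lost: d(1−F).

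Worked case, d = 50% in both arms:
- X: (130.5 + 165.8)/(0.822 + 0.089) = 325.1
- Y: (137.7 + 277.7)/(0.743 + 0.128) = 476.5
- Ratio: 476.5/325.1 = 1.47

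| Discard of nets beyond limit, X v Y | Mean area among available nets, X v Y (cm²) | Ratio Y/X | Nets lost, X v Y |
|---|---|---|---|
| none | 462.0 v 693.0 | 1.50 | 0 v 0 |
| 50% v 50% | 325.1 v 476.5 | 1.47 | 8.9% v 12.8% |
| 70% v 70% | 262.6 v 371.0 | 1.41 | 12.4% v 18.0% |
| 90% v 90% | 194.8 v 251.3 | 1.29 | 16.0% v 23.1% |
| 30% v 70% | 383.0 v 371.0 | 0.97 | 5.3% v 18.0% |
| 70% v 30% | 262.6 v 570.4 | 2.17 | 12.4% v 7.7% |

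The share of all nets that is present and serviceable is 82.2% v 74.3% in every row. This follows by construction, because only nets beyond the limit are discarded here.

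**Check on a torn/intact scale.** Let t be the torn share of all nets, and dT and dI the discard probabilities of torn and intact nets. The torn share among available nets is t(1−dT) / [t(1−dT) + (1−t)(1−dI)]. Assume t = 20% v 35%, a ratio of 1.75.
- Every net has the same 20% chance of loss: the shares stay 20% v 35%, so there is no bias.
- Equal discard of torn nets at 30%, 50% or 80%, with dI = 10%: ratio 1.81, 1.89 or 2.03. The difference falls from 15 points to 13.2, 10.8 or 5.4 points.
- Torn nets discarded 30% v 70%, with dI = 10%: 0.14/0.86 = 16.3% v 0.105/0.69 = 15.2%, ratio 0.93.
- Torn nets discarded 70% v 30%, with dI = 10%: 7.7% v 29.5%, ratio 3.84.

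The direction and size of the bias therefore depend on both the discard pattern and the scale.

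**The case against.** The strongest reply is that discarded nets do not leave the durability assessment. Survivorship and attrition belong to the same objective and are measured in the same surveys, and only net withdrawal depends on funding. In the equal-discard rows, the difference that leaves the integrity comparison reappears as a difference in loss, up to 23.1% v 16.0%. Reporting the two side by side is transparent, and a composite cannot separate fabric failure from disposal habits. On the hole-area scale, equal discard of 50% to 70% moves the ratio only from 1.50 to 1.47 or 1.41.

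Much of this stands. A reader might infer that the plan ignores lost nets, or that a real durability difference will be hidden. The documents support neither. Loss is a planned measure, and the bias has no fixed direction. Nor does the text limit the sample to nets that are hanging: it speaks of nets withdrawn from households, so a stored net is not excluded.

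The side-by-side reading is nevertheless not secured. Survivorship is absent from 13.1 and 13.5, so hole number and area is the physical-durability outcome that has a stated between-arm analysis. The household ownership and coverage outcomes do not follow the campaign nets received. Nothing tells the analyst to read integrity in the light of loss.

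Two things cannot be checked: the questionnaire (Appendix F) is not available, so reasons for net loss may already be asked, and neither is the WHO guidance the protocol cites for durability.

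**Conclusion.** The point holds as a minor one. The integrity comparison conditions on a net still being available, and no stated analysis links it to loss. If discarding depends on damage, the planned ratio can be attenuated (1.50 to between 1.47 and 1.29 with equal discard), reversed (0.97) or exaggerated (2.17). If loss is unrelated to damage, it is unbiased. These sizes rest wholly on the assumed distribution, limit and discard rates; they show what is possible and do not predict this trial's result.

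The outcome is secondary, depends on funding and is not in the SAP. The primary outcome is unaffected. It would be too strong to say that the economic evaluation rests on this comparison: section 10.1 models an expected 3-year lifespan, shorter lifespans are optional additional analyses, and nothing limits their durability data to hole counts.

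**What to change.** In Protocol 13.1 and 13.5, and in the SAP if this component is to be analysed there:
- Add as the main between-arm durability comparison the proportion of campaign nets received that are still present and serviceable, with a pre-specified hole-area or hole-index limit.
- Count nets lost to damage as failures, and state how nets lost for other reasons enter the denominator.
- Take nets received from the household questionnaire or the distribution register, since the electronic campaign system already covers "allocation of number of LLINs for each household". Combine survey survivorship with the serviceable share among sampled nets. As one net is taken per household, weight each by the number of campaign nets present there.
- Report survivorship by arm beside it, with a stated model.
- Keep hole number and area among available nets as a descriptive result, labelled as conditional on survival.
- Record the reason for loss, if it is not already asked.
- State what happens when a selected household has no campaign net left.

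The cost is protocol wording, a serviceability limit fixed in advance, and at most one questionnaire item. No extra nets need to be withdrawn.

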9.2 Net integrity

Net integrity will be assessed using standard WHO guidelines [56]. The nets will be assessed by counting the number of holes (including tears in the netting and spilt seams) by their location on the net and their size.

Holes will be classified into the following categories:

- Smaller than a thumb (0.5-2cm)
- Larger than a thumb, but smaller than a fist (2-10cm)
- Larger than a fist, but smaller than a head (10-25cm)
- Larger than a head (>25cm)

Holes less than 0.5cm will be ignored. Evidence of repairs to the net fabric and the type of repair will be noted and recorded. Net use, care and repair will be emphasised as part of this process. Novel net durability assessment procedures are being developed by a number of transnational research groups and may be incorporated into the LLIN integrity assessments. The new assessments will not affect net replacement, measurement, or storage protocols.

9.3 Chemical analysis of LLINs

If resources are available, HPLC will be conducted on samples of nets taken from the top surface of the LLINs withdrawn at the 24-month timepoint. The insecticides deltamethrin, alphacypermethrin, and pyriproxyfen, and the synergist PBO, will be extracted from the net samples using standard solvent extraction protocols, as in prior studies [54]. The chemicals extracted from the net will then be filtered to remove impurities before quantitative analysis performed via HPLC using controls of known insecticide concentration. This will allow the total concentration of insecticide and or synergist remaining on each net to be measured. Comparison to results of HPLC analysis on unused nets from the same distribution batch will allow the chemical degradation of the nets to be determined.

10 Economic evaluation

10.1 Overview

An economic evaluation will be conducted to compare the incremental costs and cost-effectiveness of LLIN strategies using either Royal Guard LLINs or PBO LLINs in accordance with the reference case for economic evaluations in low- and middle-income countries [57]. The analysis will combine primary data on costs and effectiveness from the trial with additional secondary data to inform policy choices regarding the choice of LLIN. The analysis will take a disaggregated societal perspective, meaning that it will include costs to households, the health service, and donors, separately and together [57]. Research costs will not be included in the cost-effectiveness analyses. Efficiency will be measured in incremental cost-effectiveness ratios. A decision tree will be used to calculate the incremental cost-effectiveness of the Royal Guard LLIN compared to PBO LLINs [58, 59]. Parameter values for the model will include effectiveness inputs, cost inputs, probability inputs, and payoffs [60]. Implementation will be modelled over the expected 3-year lifespan of the LLINs, and costs and outcomes of malaria episodes occurring in these three years will be modelled over a lifetime horizon [61, 62]. Additional analyses may be conducted using a shorter lifespan for one or both of the nets based on durability data. Where possible, the parameter values will be directly measured during the clinical trial. For values that cannot be directly measured, estimates will be derived from the literature and other relevant sources. In addition, a Markov model will be explored as a possible alternative method of assessing the cost-effectiveness of the LLINs. Markov models are useful for decision problems involving risks that change over time and events which may occur more than once [63, 64]. Unlike the decision tree model, which is linear and assumes that different outcomes are mutually exclusive, a Markov model is well-suited for analysis of LLIN interventions, which can capture repeated malaria episodes. The main outcome will be cost in USD per disability-adjusted life-year (DALY) averted and per malaria case averted. The incremental cost per DALY averted will be compared to plausible cost-effectiveness thresholds [65].

10.2 Estimation of costs

The financial and economic costs of LLIN distribution will be estimated using the ingredients approach with quantities and values reported separately (Appendix J) [66]. Economic costs capture opportunity costs, recognizing that the cost of using resources means that these resources are unavailable for productive use elsewhere. Economic costs include direct and indirect costs to the LLIN provider and recipient, and reflect the full value of resources used to implement the net campaign including those which do not incur a financial cost to the health service such as donated goods or services and time required of household members or village health team workers (VHT). There are two main components of cost to be considered in malaria economic evaluations, the cost of the intervention and the cost savings from averted cases of malaria. The total cost of intervention is represented by the following equation:

$$\text{Total cost} = \text{cost of intervention} - \text{cost saving from cases averted}$$

